HRA Health Research Authority
ICF Informed Consent Form

ISRCTN International Standard Randomised Controlled Trials

Number

NHS R&D National Health Service Research & Development

NIHR National Institute for Health Research

NMS New Medicines Service
PI Principal Investigator
PCN Primary Care Network

PIS Participant Information Sheet

PPIEP Patient & Public Involvement, Engagement &

Participation

PREM Patient-Reported Experience Measure
PSRC Patient Safety Research Collaborative

QoL Quality of Life

RCT Randomised Control Trial
RfPB Research for Patient Benefit
REC Research Ethics Committee
WHO World Health Organisation

WP Work Package

My Medicines Journey: Assessing the feasibility and implementation of a Toolkit

iii. STUDY SUMMARY

Study Title	Assessing the feasibility and implementation of the 'My medicines journey' intervention: A multi-methods evaluation		
Internal ref. no. (or short title)	My Medicines Journey: Assessing the feasibility and implementation of a Toolkit.		
Clinical Phase			
Study Design	Feasibility study		
Study Participants	Older people living with frailty and one or more long-term conditions and who have had one or more changes to their medicines during admission.		
	Family carers		
	Hospital staff (pharmacy teams) and community pharmacists implementing the intervention.		
Planned Size of Sample (if applicable)	Phase 2: 168 older people (84 to receive intervention; 84 to act as 'control' to determine if it is feasible to collect outcome measures from a non-trial group)		
	20 Older people/informal carers for qualitative interviews		
	12 Hospital staff for qualitative interviews		
	Up to 8 Hospital Staff for the Focus group/feedback sessions.		
Treatment duration	2 weeks post-discharge		
Follow up duration	3 months post-discharge		
Planned Study Period	24 months		
	Objectives	Outcome Measures (feasibility)	
Primary	Validate a PREM Explore the acceptability of implementation of the PREM from the perspectives of patient participants and staff	 Rate of recruitment Loss of follow-up at 2 months Intervention delivery Participation engagement with the intervention Evidence of feasibility to collect outcome measures 	
Secondary	Consolidate RCT protocol and refine outcome measures.		
	Create a multi-site trial protocol		

My Medicines Journey: Assessing the feasibility and implementation of a Toolkit

V. FUNDING AND SUPPORT IN KIND

FUNDER(S) (Names and contact details of ALL organisations providing funding and/or support in kind for this study)	FINANCIAL AND NON-FINANCIAL SUPPORT GIVEN
NIHR	£244,861.00 Staff costs Travel, Subsistence & Conference Costs Equipment Costs Consumables PPIEP Costs Dissemination costs
University of Bradford	 Venues for meetings

v. ROLE OF STUDY SPONSOR AND FUNDER

The study funder will provide financial support for all study aspects, including Staff Travel, Subsistence and conference Costs, Equipment Costs, Consumables, PPIEP Costs, and Dissemination costs. The study sponsor, on the other hand, will provide administrative support, including indemnity for the study and managing study data. However, the sponsor and funder do not have any role in the study design, conduct, data analysis and interpretation, and dissemination of results.

vi. ROLES AND RESPONSIBILITIES OF STUDY MANAGEMENT COMMITTEES/GROUPS & INDIVIDUALS

Study Management Committees

1. Patient & Public Involvement Group

Our PPI group will:

- Provide expert patient opinion during project design, especially ethical considerations, protocol development, recruitment strategy, and piloting data collection tools.
- o Co-design participant documentation.
- Co-facilitate hospital and community pharmacy staff focus groups to review findings (with training).
- o Produce newsletters reporting project progress for participants and sites.
- \circ Help to problem-solve issues as they arise.
- Develop ideas for dissemination.

My Medicines Journey: Assessing the feasibility and implementation of a Toolkit

vii. Protocol contributors

This protocol has been developed with input from an experienced team with an appropriate mix of academic, clinical, and research delivery skills who have worked successfully on medicines optimisation and older people research programmes. These include;

- [name] who is the study Chief Investigator and grant Lead Applicant. She contributed to developing the grant application, which is the basis of this study protocol.
- [name]
- [name]
- [name] (PPI representative)
- [name]
- [name]
- [name]
- [name]
- In addition, the protocol and other study documents, such as the PIS, ICF, and data collection tools, benefited from the input of members of the public, who provided feedback on different aspects, such as the terminology used through the PPIEP. The PPIEP members also provided patient opinions on ethical considerations and risk assessment.

My Medicines Journey: Assessing the feasibility and implementation of a Toolkit

viii. KEYWORDS: Older people

Medicines

Management

Intervention

Feasibility

Multi-methods

My Medicines Journey: Assessing the feasibility and implementation of a Toolkit

ix. STUDY FLOW CHART

Phase 1 (Completed)

- Development of a Patient Reported Experience Measure (PREM)
- Pilot and revise the questionnaire with 20 stakeholders
- This Phase has been completed

Phase 2

- Pre-test, post-test feasibility study
- Older people complete questionnaires at three-time points to measure patient experience (WP1 PREM) and healthcare utilisation
- Post-intervention semi-structured interviews to explore barriers and enablers to intervention use

Phase 3

 Consolidate implementation strategy and multi-site trial protocol My Medicines Journey: Assessing the feasibility and implementation of a Toolkit

1 BACKGROUND

Harm from medicines during care transitions is a significant patient safety issue globally. The World Health Organisation (WHO) has set a target to reduce medicines-related harm by 50% by 2022, prioritising medicines safety for high-risk individuals and complex situations (Donaldson et al., 2017). While various methods exist to address medicines-related problems, only a few have been implemented in routine clinical practice (Liew et al., 2020). Despite the availability of professional services such as medicines reconciliation and medication reviews, medicines-related harm continues to be a widespread concern (WHO, 2024).

Older people, particularly those with long-term conditions, multiple medicines (polypharmacy), and frailty, are at a high risk of experiencing harm from medicines during transitions in care. Examples include adverse drug reactions and medicine errors, resulting in hospital readmission. Research indicates that 1 in 3 older people experience medicines-related harm within eight weeks of hospital discharge, amounting to an estimated cost of £396 million annually for the NHS (Parekh et al., 2018). Furthermore, studies involving older patients and their family caregivers have highlighted various gaps in the care received, including inadequate verbal and written communication about medicines, insufficient support for developing self-management skills, and a lack of person-centred follow-up. These challenges have been linked to a lack of knowledge, confidence, and capability for safe and effective post-discharge medicines management among patients, including older people (Fylan et al., 2018; Tomlinson et al., 2020a).

Ryan et al. (2014) argue that appropriately designed, theory-driven, complex interventions, such as medication self-monitoring and self-management programmes, can improve medicine use, adherence, and clinical outcomes and reduce adverse events. Additionally, a scoping review found evidence suggesting that pharmacist interventions within multidisciplinary teams provide greater clinical and economic benefits compared to standard care (Delgado-Silveira et al., 2021). There were significant reductions in emergency department attendance, primary care visits, hospital readmission rates, and length of hospital stay. Despite this compelling evidence, more work is needed in this area.

This feasibility study is based on our previous NIHR RfPB-funded project (PB-PG-0317-20010), which examined the patient experience of managing medicines after hospital discharge. We co-designed an intervention named 'My Medicines Journey', using the Theoretical Domains Framework to address medicines-related problems for older individuals with long-term conditions. This pharmacy-led intervention involves better quality medicines conversations, increased knowledge, skills, and self-management to ensure continuity of medicines-related care. It begins during hospital admission, led by the hospital pharmacy team, and continues after discharge with the community pharmacy-led Discharge Medicines Service (DMS). The multi-component intervention includes a patient information resource (paper-based), video, medicines support reviews, self-management planning, and patient-held checklists.

Our primary focus is on older people as they are a public health and NHS priority, frequent service users, and susceptible to deficiencies in medicines management. After conducting a systematic review of 24 studies that promoted continuity of medicines management (Tomlinson et al. 2020b), we found that interventions were more likely to reduce hospital readmission rates if they bridged the care transition and included components of self-management, medicines reconciliation, and telephone follow-up. Our intervention incorporates these important elements. Our review also highlighted that outcome measures typically focused on healthcare utilisation, quality of life, and medicines-related problems.

My Medicines Journey: Assessing the feasibility and implementation of a Toolkit

However, no patient-reported experience measure (PREM) is currently associated with post-discharge medicines management, making it difficult to establish whether an intervention improves patient/carer experiences. This study will focus on developing and validating a PREM as a candidate primary outcome for subsequent trials. We will also test the use of other more routinely collected and validated measures that could be used as primary outcomes.

Community pharmacies could perform an important role in securing medicines continuity after hospital discharge, but few previous studies have actively involved them, and in most, they have been passive recipients of discharge medicines lists (Lussier et al. 2020). In England, community pharmacies offer NHS services, such as the DMS and the new medicines service (NMS), to support post-discharge medicines management, but this provision is challenging due to the lack of integration of community pharmacy into NHS information systems and poor patient engagement (Lam et al. 2019, Nazar et al. 2021). Our intervention includes a community pharmacy-led follow-up component (via DMS), and our study will generate evidence about the uptake of community pharmacy services. As part of the DMS, community pharmacies can refer to PCN pharmacists. Where PCN or practice pharmacy staff reconcile medicines post-discharge, there is a risk of duplication with the DMS, and we will explore how the interaction between community pharmacy and primary care pharmacy works during our study.

2 RATIONALE

It is an NHS priority to support people to age well, and for many people the focus should be to help them and their carers access tools to self-manage their conditions (NHS England, 2021). Better-managed medicines will optimise health and quality of life and reduce adverse outcomes. This, in turn, should reduce avoidable hospital readmissions and delay requirements for assisted living. The NHS has estimated that £530 million/year could be saved by improving healthcare utilisation due to avoidable medicines-related harm (NICE, 2015). This project also aligns with the 'supporting safe care in the home' theme of our Yorkshire and Humber NIHR Patient Safety Research Collaborative (PSRC).

As mentioned above, this feasibility study builds on NIHR RfPB-funded work (PB-PG-0317-20010), which explored post-discharge medicine management and co-designed an intervention. The intervention, called 'My Medicines Journey,' is pharmacy-led and multi-component. It promotes continuity of medicine-related care for older people living with long-term conditions through better-quality medicine conversations, increased knowledge, skills, and self-management.

2.1 Research aims and objectives

This multi-method study aims to assess the feasibility of implementing our intervention within the current NHS provision and explore how contextual factors influence its uptake. This will inform the development of a subsequent multi-site randomised controlled trial (RCT) to test the intervention's effectiveness and cost-effectiveness.

2.2 Specific objectives:

Although the project has three phases, this protocol and ethics application specifically relates to phase two, which aims to:

i) Explore the acceptability of implementation from the perspectives of patient participants and staff

My Medicines Journey: Assessing the feasibility and implementation of a Toolkit

- ii) Develop materials for estimating the healthcare resource use of participants, the costs of the intervention, and the subsequent resources in both arms of a RCT
- iii) Assess the feasibility of collecting a range of outcome measures
- iv) Identify local individual/ organisational barriers and enablers to intervention delivery

3 OBJECTIVES AND OUTCOME MEASURES/ENDPOINTS

3.1 Primary objective

This study aims to assess the feasibility of implementing our intervention within the current NHS provision and to explore how contextual factors influence its uptake.

Objectives:

- i) Validate a Patient-Reported Experience Measure (PREM) (developed in Phase 1 of our work)
- ii) Explore the acceptability of implementation
- iii) Assess the feasibility of collecting a range of outcome measures
- iv) Identify local individual/ organisational barriers and enablers to intervention delivery
- v) Consolidate and refine intervention components and implementation plan

3.2 Secondary objectives

To develop a subsequent protocol for a multicentre RCT.

3.3 Outcome measures

The primary outcome of this phase is the PREM validation and an understanding of the feasibility of implementing the intervention (i.e., are progression criteria met). However, the study has several outcome measures, including healthcare utilisation, medicine-related problems, self-efficacy, quality of life, and adherence.

4 PHASE TWO STUDY DESIGN

This is a feasibility study of a co-designed intervention called the 'My Medicines Journey' toolkit. The aim is to support older people to better manage their medicines after being discharged from hospital. The intervention will be initiated in the hospital and continued after discharge with the patient's community pharmacy.

The intervention will be led by the pharmacy team and is designed to optimise existing processes rather than add more tasks for the team. However, both older people and pharmacy teams will play crucial roles in implementing the intervention.

- For the patient: They will be provided with information resources to prepare them to discuss their medicines with the pharmacist. They will also receive a checklist of what they need to know before discharge.

My Medicines Journey: Assessing the feasibility and implementation of a Toolkit

- For the pharmacy team: They will be expected to ask the patient about their medicines management/support needs at home, complete a short action plan with the patient for managing their new medicines at home, and, if possible, allow the patient to self-administer one or two doses before going home so they can practice, and transfer information to the community pharmacy to initiate DMS.

A non-intervention arm (n=84) will be recruited to explore whether the outcome measures can be collected from a 'control' group (n=84) to inform the future trial and boost our questionnaire sample size to enable PREM validation. This arm will receive usual care for that hospital ward but will additionally be asked to complete outcome measure questionnaires (e.g., baseline data, PREM, EQ-5D-5L, healthcare utilisation).

This feasibility study aims to test if the pharmacy team can incorporate the intervention into their regular work, assess the positive and negative impacts of doing so, and determine whether progression criteria (see page 24 for more details) are met, which would indicate a move to full trial. We will ask four NHS sites, including Bradford Teaching Hospitals NHS Trust, Hull University Teaching Hospitals NHS Trust, Leeds Teaching Hospitals NHS Trust, and Calderdale and Huddersfield NHS Trust, to each recruit approximately 21 older people over a span of 12-16 weeks period, which averages out to approximately 2 older people per week (n= 84), but with attrition, we predict a smaller final sample size. Based on previous feasibility studies, such as Teare et al. (2014) who determined that 70 measurable subjects are required when outcomes are continuous, we believe this is an appropriate sample size to determine feasibility.

We will also conduct observations with the team, distribute staff questionnaires, and conduct semi-structured interviews with individuals who have used the intervention.

In summary, phase two of the study will involve:

- Administering the PREM questionnaire, developed in phase one, to assess postdischarge medicine experiences with older people, carers, and health professionals and to test its usefulness.
- We will work with approximately 4 local hospitals and participants' community
 pharmacists to use our Toolkit with older people and their carers. We will assess how
 well it works and its acceptability by using questionnaires, observations and
 interviews. In addition, we shall work with 4 other local hospitals to recruit a control
 group that will be asked to complete patient surveys, including PREMs, EQ5D5L,
 baseline data, healthcare utilisation, adherence, self-efficacy, and DRPs.
- Finally, we will use the findings to enhance the intervention Toolkit and implementation strategy and develop a proposal for a large-scale multi-site trial.

The workflow chart below summarises all components of the study design for the second phase of my medicines journey project.

My Medicines Journey: Assessing the feasibility and implementation of a Toolkit

Study set-up

PREM Refinement

Site recruitment (4 sites for the intervention group and 4 sites for the control group)

Participant recruitment [168 older people, 84 for the intervention arm (21 per site) and 84 for the control group (21 per site)]

Intervention arm delivery

Materials to help older people manage their medicines (e.g., family carer packs and checklist)

Data collection: Questionnaires [(2 weeks (PREM 1, outcome measures x 5) and 3 months (PREM 2 & outcome measures x 5) post-discharge)]

Control arm delivery

Questionnaires at same time points as intervention arm (PREMs, EQ5D5L, baseline data, healthcare utilisation, adherence, self-efficacy, MRPs)

Assessment of feasibility

Documentary analysis/ routine data collection
Staff observation (various times over 8 weeks at each site)
Interviews with older people/carers (n=20)
Staff survey (n=30)
Staff Interviews (n=12)
Focus Group meetings (8 Hospital staff)

Synthesis and refinement

Findings
Refine outcome measures
Create a multi-site trial protocol

My Medicines Journey: Assessing the feasibility and implementation of a Toolkit

STUDY SETTING AND METHODS OF DATA COLLECTION AND DATA ANALYSIS

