5.3 STATISTICS AND DATA ANALYSIS

5.3.1 Sample size calculation

We plan to recruit a diverse sample of 168 older people across 4 intervention sites and 4 control sites during hospital admission, plus hospital staff involved in delivering the intervention across the sites.

There are four varying sample size estimates for this study:

My Medicines Journey: Assessing the feasibility and implementation of a Toolkit

- A. To determine feasibility against the progression criteria (n=84 intervention participants) The sample size is based on the need to understand whether it is possible to consistently recruit 2 participants a week for up to 16 weeks per site and account for attrition. Based on previous feasibility studies, such as Teare et al. (2014) who determined that 70 measurable subjects are required when outcomes are continuous, we believe this is an appropriate sample size to determine feasibility against our progression criteria.
- B. To determine if data can be collected from a 'control' arm (n=84 control participants) Sample size is determined based on A, and contributes to C.
- C. To validate the PREM (n=168 patient participants)

 For validation studies, a widely used rule of thumb suggests 10 responses per item in the instrument.

The PREM contains 15 to 18 items, leading to a sample size in the range of 150 to 180.

The intended sample size is 168.

If this is achieved, the margin of error (for responses to each item) will be:

- A) +/- 7.5% assuming a proportion of 50% at the 95% confidence level
- B) +/- 5% assuming a proportion of 50% at the 80% confidence level

We consider this to be acceptable.

Extreme responses to the items (proportions higher or lower than 50%) will reduce the margin of error.

D. To collect in-depth qualitative data from a smaller sample of patient and staff participants (n=12-30 depending on methods)

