5.3.2 Planned recruitment rate

We have worked with sites to understand what is realistic, given current workforce pressures and research timelines. Therefore, the planned recruitment rate is 2 participants per week for up to 16 weeks.

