5.3.3.2 Analysis of the Intervention Outcome Measures

We shall focus on descriptive statistics such as percentages, means and standard deviations to understand the key features of the data from the outcome measures (Healthcare utilisation, Medicine-Related Problems, Self-efficacy, QoL, and Adherence) and the staff survey.

Criteria to determine if the intervention should proceed to RCT will be refined in agreement with our project advisory board. We will apply 'Red', 'Amber', and 'Green' (RAG) criteria (Young et al., 2019), which we have previously applied in our work (ISCOMAT programme RP-PG-0514-20009). Key criteria will be based on recruitment, intervention delivery, and participant engagement:

Criteria	Green	Amber	Red
Rate of recruitment	2 participants per week per site	1 participant per week per site	0 participant per week per site
Loss to follow up at 2 months	<20%	21-35%	>35%
Intervention delivery >50% on fidelity rating scale	100%	50-99%	<50%
Participant engagement with intervention (use of checklist, self-management plan and engages with DMS)	>75%	40-74%	<40%
Evidence of feasibility to collect outcome measures	>75%	35-75%	<35%

We will regularly review progress against the RAG progression criteria at project meetings and assess whether these are achievable within a full trial. Where progress is 'amber', barriers to implementation should be resolvable and we will work with our project advisory group (PAG) to review and adapt methods within the feasibility study. If more than 50% of our RAG criteria result in 'red' scores, we will not progress to a further full trial.

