7.1.2 Size of sample

We aim to recruit a diverse sample of 168 older people from eight hospitals. We will recruit 84 older people for the intervention group from 4 sites and another 84 for the control group from 4 different sites. We aim to recruit 21 participants from each site, with a goal of enrolling two older people per week. This sample will yield sufficient data to meet the objectives of this phase. The hospital staff involved in the intervention delivery will be recruited across the four hospital sites. We aim to recruit up to 30 diverse staff members across all sites for the survey work and 12 for subsequent interviews.

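### The per-site target, recruitment window and weekly rate do not agree, and the recruitment progression row has single values with no limits between them

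*Protocol*

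**What the plan says.** Section 4 asks each of the four intervention sites to "each recruit approximately 21 older people over a span of 12-16 weeks period, which averages out to approximately 2 older people per week". Section 7.1.2 applies the same pair of figures to all eight sites: "We aim to recruit 21 participants from each site, with a goal of enrolling two older people per week".

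The weekly rate recurs in two other places. Section 5.3.1, part A, bases the 84 intervention participants on the need to learn "whether it is possible to consistently recruit 2 participants a week for up to 16 weeks per site and account for attrition". Section 5.3.2, after noting that sites were consulted on what is realistic, states that "the planned recruitment rate is 2 participants per week for up to 16 weeks".

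In the progression table of section 5.3.3.2, Green for recruitment is "2 participants per week per site", Amber is one participant per week per site, and Red is "0 participant per week per site". The same section says the study will not go on to a full trial if more than half of the criteria are Red, and that the criteria will be refined with the project advisory board. Section 3.3 makes meeting the progression criteria part of the primary outcome of this phase.

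**The concern.** Three quantities describe one plan: the number per site, the weeks available and the rate per week. Any two fix the third, and the three stated values are not compatible.

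This would be a slip of wording if the rate were not also the Green value of a progression criterion. Because it is, a site can do what section 4 asks of it and still miss Green.

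The row also names three points on a continuous scale and does not say where one colour ends and the next begins. Average rates are almost never exactly 2, 1 or 0, so most sites would have no defined colour. Whoever scores the row would have to choose a rule after seeing the data, for a result that belongs to the primary outcome.

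**Working it through.** **Inputs.** Target of 21 per site (sections 4 and 7.1.2). Window of 12 to 16 weeks (section 4). Rate of 2 per week (sections 4, 5.3.1, 5.3.2 and 7.1.2). Green 2, Amber 1, Red 0 per week per site; five criteria; no full trial if more than 50% are Red (section 5.3.3.2).

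**Step 1: the plan's own figure.** Rate = target / weeks. The stated result is about 2.

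| Weeks to reach 21 | Rate per week | Colour on the table as written | Colour if rounded to the nearest whole number |
|---|---|---|---|
| 12 | 21/12 = 1.75 | between Amber and Green | Green |
| 13 | 21/13 = 1.62 | between Amber and Green | Green |
| 14 | 21/14 = 1.50 | between Amber and Green | Green, only if a half is rounded up |
| 15 | 21/15 = 1.40 | between Amber and Green | Amber |
| 16 | 21/16 = 1.31 | between Amber and Green | Amber |

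No point in the window gives 2. The word approximately might cover 1.75; it does not cover 1.31, which is nearer to 1.

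**Step 2: the inverse checks.** Weeks = target / rate = 21/2 = 10.5, below the 12-week lower end of the window. Number per site = rate × weeks = 2 × 12 = 24 at the lower end, already above 21. The consistent pairs are therefore 21 at 2 per week in 10.5 weeks, or 21 in 12 to 16 weeks at 1.75 to 1.31 per week.

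**Step 3: the lower end of the scale.** Take a site with 3 recruits in 16 weeks: 3/16 = 0.19 per week, and 3/21 = 14% of target. Read literally, Red is a rate of 0, so this site is not Red; a single recruit (1/16 = 0.06) is enough to avoid it. With rounding to the nearest whole number, Red would be a rate below 0.5, that is, fewer than 0.5 × 12 = 6 recruits in 12 weeks or fewer than 0.5 × 16 = 8 in 16 weeks. The same site would then be Red. The table does not say which reading applies.

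**Step 4: link to the stop rule.** More than 50% of five criteria means at least three Reds (2/5 = 40%, 3/5 = 60%). If recruitment is Red only when nobody is recruited, three of the other four criteria must in effect be Red for the rule to act.

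**The case against.** The best defence is that the figures are loose on purpose. Both the 21 and the 2 are described as approximate, whole-number categories invite rounding, and the criteria are declared open to refinement. A statistical analysis plan, not available here, might also set the limits. Part of this stands: with rounding, a site that finishes in 12 or 13 weeks is Green, and so is one at 14 weeks if a half is rounded up. But no rounding rule is stated, and under that rule an on-plan site taking 15 or 16 weeks is still Amber. Later refinement does not remove a contradiction between sections of the protocol, and limits chosen once recruitment is known lose much of their value.

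Three stronger readings are tempting, and the documents do not support them.

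- A reader might infer that 2 per week for 16 weeks means 32 per site, so that the planned 84 falls well short of 2 × 16 × 4 = 128. Sections 5.3.1 and 5.3.2 say *up to* 16 weeks. That is a ceiling, and a site that stops at 21 after 10.5 weeks is within it. No such total is planned.
- A reader might infer that Red can never occur and that recruitment can never contribute to stopping. This holds only on the literal reading. With rounding Red is reachable, and the other four criteria can trigger the stop rule on their own.
- A reader might want a probability that a site on plan reaches Green. The protocol gives no recruitment distribution and no rule for pooling sites, while the criterion is per site. Any such figure would reflect the assumptions chosen for it.

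**Conclusion.** The point holds as an internal inconsistency together with an incompletely specified decision row. The planned 21 in 12 to 16 weeks corresponds to 1.75 to 1.31 per week, 12.5% to 34% below the stated 2 (1 − 1.75/2 and 1 − 1.31/2). On the table as written, a site meeting its target anywhere in the window has no colour. With rounding to the nearest whole number it is Amber at 15 to 16 weeks. On the literal reading, very poor recruitment short of zero is not Red.

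The arithmetic uses only the protocol's figures. What follows for scoring depends on the unstated reading of the bands, and for that reason both readings are shown. This should be fixed before recruitment is scored. It does not call the sample of 84 per arm or the choice of sites into question.

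**What to change.** Before any recruitment is scored, make sections 4, 5.3.1 (part A), 5.3.2, 7.1.2 and the table in 5.3.3.2 use one consistent set of target, window and rate. Define the score as recruits divided by weeks open to recruitment, for each site, until the target is reached. Make the bands contiguous.

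The simplest version keeps the rate that section 5.3.2 reports after discussion with sites:

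- Window: about 10.5 weeks expected at the planned rate, with 16 weeks as the maximum.
- Green: at least 2 per week per site.
- Amber: 1 to below 2.
- Red: below 1.

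Alternatively, if 21 in 12 to 16 weeks is the real plan, restate the rate as 1.3 to 1.75 per week per site and set Green from that target. The Amber/Red limit should then be agreed with the advisory board, because the documents give no basis for a particular value.

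The cost is wording in four sections and one table row. The sample, sites and data collection do not change.
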